4.1 Description of study design

This is a Phase II, open label, single arm, multicenter study of INC280 administered orally as first-line treatment in patients with advanced HCC. See [Figure 4-1](#) for an overview of the study design.

Patients will be enrolled into the study in 2 parts (Dose-Determining and Dose Expansion parts) where the first Part will allow the assessment of safety and PK profiles prior to initiating a larger second Part.

Figure 4-1 Study design

* The rules for dose recommendation for the Dose Expansion Part will be followed as listed in [Table 6-1](#).

A complete treatment cycle is defined as 21 days of continuous dosing, with the first dose of the INC280 defining Day 1 and the last day of a complete treatment cycle being Day 21. In the Dose-Determining Part, the qualifying AEs for dose determination will be assessed for the first 28 days of treatment for comparability to Cycle 1 safety data observed in previous/ongoing clinical trials.

Molecular pre-screening

Evidence of dysregulation of c-MET pathway is required in order to begin screening activities.

Evidence can be demonstrated by submission of an archival or a newly obtained HCC tumor sample to a central laboratory for analysis. Tissue requirements are found in [Section 7.1.1.2](#).

Patient must sign the molecular pre-screening consent to allow for the collection and submission of samples to the central laboratory for analysis.

If the results of the central analysis meet the criteria for c-MET positivity ([Section 5.2](#)), the patient can proceed with the screening procedures. In exceptional cases, patients with a tumor harboring a documented cMET mutation (based on the results of local testing) can be enrolled in the study following discussion and agreement with Novartis.

Screening period

When the required c-MET status is known, patients will sign the Main Informed Consent Form and will be evaluated against study inclusion and exclusion criteria and safety assessments ([Table 7-1](#)). Eligible patients will begin study treatment within 14 days of the commencement of the screening assessments.

Dose-Determining Part

During the Dose-Determining Part, at least six patients will be enrolled and treated with INC280 at 300 mg bid (capsule). Safety, full PK profiles of INC280 on Cycle 1, Days 1, 2, 15 and 16, predose PK samples on Cycle 2 Day 1 and Cycle 3 Day 1, demographics and other baseline characteristics will be collected in these patients ([Section 7.1.2.3](#), [Section 7.2.2](#) and [Section 7.2.3](#)).

A dose decision analysis based on safety and PK data will be conducted when patients from Dose-Determining cohort have completed 28 days treatment and data from at least 6 patients are evaluable for the dose-determining set (DDS) (see [Section 10.1](#)). The analysis will be guided by the medical review of available clinical, laboratory, and PK data, as well as the recommendation from the Bayesian Logistic Regression Model (BLRM) (see [Section 6.2.2](#) for details on the decision process).

Novartis and the principal investigators will have a dose decision meeting to discuss and evaluate the data. At this meeting, Novartis and the principal investigators must reach consensus on the dose level to be used in the Dose Expansion Part. Novartis will prepare minutes from this meeting and circulate them to each investigator for comments prior to finalization. The Expansion Part dose will be communicated to all investigators in writing.

Patients in the Dose-Determining Part who have not experienced a dose reduction will be allowed to switch to the confirmed Expansion Part dose, if different from the Determining Part dose, under consultation from the Investigator with Novartis.

Dose Expansion Part

Once the Expansion Part dose has been confirmed, approximately 50 patients in total will be enrolled, among which around 25 to 40 patients will have the c-MET positive status as specified in the inclusion criteria ([Section 5.2](#)).

Detailed information on all patients will be collected and reported (see [Section 10](#) for details).

Follow-up

All patients will be followed-up as described in [Section 7.1.5](#). At minimum, patients must complete the safety follow-up assessments 30 days after the last dose of the study treatment.

All patients will be followed until progressive disease (PD), death or withdrawal of consent regardless of any drug discontinuation. All patients will be followed for OS for a duration of at least 6 months after last patient first dose.

4.2 Timing of dose decision analyses and design adaptations

The safety and PK analysis will be conducted when at least six patients enrolled in the Dose-Determining Part become evaluable for the DDS.

4.3 Definition of end of the study

The end of study will be the earliest occurrence of one of the following:

- completion of the survival follow-up period and the Study Phase Completion page for the last patient treated with INC280
- or the study is terminated early
- or another clinical study becomes available that can continue to provide study treatment in this patient population; all patients ongoing are transferred to that clinical study and all discontinued patients have completed the safety follow-up period. The follow-up for disease progression and survival will not be performed or pursued (See [Section 7.1.5](#))

At the end of the study, every effort will be made to continue provision of study treatment outside this study by an alternative way, to patients who, in the opinion of the investigator, are still deriving clinical benefit.

4.4 Early study termination

The study can be terminated at any time for any reason by Novartis. Should this be necessary, the patient should be seen as soon as possible and the same assessments should be performed as described in [Section 7.1.4](#) for a prematurely withdrawn patient. The Investigator may be informed of additional procedures to be followed in order to ensure that adequate consideration is given to the protection of the patient's interests. The Investigator will be responsible for informing IRBs and/or IECs of the early termination of the study.

4.5 Rationale for public health emergency mitigation procedures

In the event of a public health emergency as declared by local or regional authorities (i.e. pandemic, epidemic or natural disaster), mitigation procedures to ensure patient safety and trial integrity may be implemented; such procedures are listed in relevant sections of the study protocol. Notification of the public health emergency should be discussed with Novartis prior to implementation of mitigation procedures, and permitted/approved by local or regional health authorities and ethics committees as appropriate.

5 Population

5.1 Patient population

Adult patients with histologically or cytologically confirmed advanced HCC which is not amenable to surgical resection or other loco-regional therapy and who have received no prior systemic therapy, are eligible. Child-Pugh classification (CPC) will be used to assess the severity of impaired hepatic function in patients with liver cirrhosis. Only patients with Child-Pugh A (5-6 point liver function) are included since more severe liver function impairment renders study patients prone to liver decompensation from underlying cirrhosis or reactivation of chronic hepatitis B viral infection potentially leading to uninterpretable study data based on heterogeneity and causality in exposure, mortality, and AEs.

Evidence of c-MET expression must be documented through central laboratory testing (see [Section 7.1.1](#) for further details). Patients enrolled in this study are not permitted to participate in additional parallel investigational drug or device studies. The investigator or designee must ensure that only patients who meet all the following inclusion and none of the exclusion criteria are offered treatment in the study.

5.2 Inclusion criteria

Patients eligible for inclusion in this study have to meet **all** of the following criteria:

1. Patients with confirmed c-MET pathway dysregulation at pre-screening as defined by:
 - c-MET IHC intensity score 3+ in $\geq 50\%$ of tumor cells
 - or c-MET IHC intensity score 2+ in $\geq 50\%$ of tumor cells only if they have in addition MET gene copy number ≥ 5 as detected by FISH
 - or MET gene copy number ≥ 5 by FISH and unknown c-MET IHC results
 - or c-MET mutation can be enrolled in the study following discussion and agreement with Novartis
2. Written informed consent must be obtained prior to any screening procedures.
3. Patients aged ≥ 18 years (male or female).
4. Patients with advanced (unresectable and/or metastatic, stage C based on Barcelona-Clinic Liver Cancer (BCLC) staging classification) hepatocellular carcinoma which would not be suitable for treatment with loco-regional therapies or have progressed following locoregional therapy such as surgical resection, percutaneous hepatic arterial embolization, radiofrequency ablation, and percutaneous interventional therapy.

5. At least one tumor lesion meeting measurable disease criteria as determined by RECIST v1.1. Lesions previously treated with local therapy, such as radiation therapy, hepatic arterial embolization, radiofrequency ablation, and percutaneous interventional therapy should not be selected unless progression is noted at baseline, in which case, these lesions would be considered as non-target lesions.
6. Current cirrhotic status of Child-Pugh class A (5-6 points) ([Appendix 2](#)), with no encephalopathy. Slight ascites controlled by diuretics is permitted in this study.
7. Availability of a representative tumor tissue specimen (archival tumor tissue is allowed) at pre-screening.
8. ECOG performance status ≤ 2 .
9. Willing and able to comply with scheduled visits, treatment plan and laboratory tests.

5.3 Exclusion criteria

Patients eligible for this study must not meet **any** of the following criteria:

1. Received any prior systemic chemotherapy or molecular-targeted therapy for HCC such as sorafenib.
2. Previous local therapy completed less than 4 weeks prior to the dosing and, if present any related acute toxicity $>$ grade 1.
3. Previous treatment with a c-MET inhibitor or HGF targeting therapy.
4. Previous treatment with yttrium-90 spheres.
5. Patients with any other malignancies within the last 3 years before study start, except for adequately treated carcinoma in situ of the cervix, basal or squamous cell skin cancer.
6. History of HCC tumor rupture.
7. Patients who have signs/symptoms attributable to portal hypertension and have not been assessed with upper GI endoscopy to rule out high-risk of variceal bleeding. If varices are identified that require intervention (banding), patient will not be eligible until varices adequately treated.
8. Patients with known active bleeding (e.g. from GI ulcers, esophageal varices) within 2 months prior to baseline/screening visit or with history or evidence of inherited bleeding diathesis or coagulopathy.
9. Clinically significant (CTC grade 3 or 4) venous or arterial thrombotic disease within past 6 months.
10. A history of acute or chronic pancreatitis, surgery of the pancreas, or any risk factors that may increase the risk of pancreatitis.
11. Patients with known brain metastasis or who have signs/symptoms attributable to brain metastases and have not been assessed with radiologic imaging to rule out the presence of brain metastases.
12. Serious, non-healing wound, ulcer, or bone fracture.
13. History of abdominal fistula, GI perforation, or intra-abdominal abscess within past 6 months prior to study treatment.
14. Clinically significant third space fluid accumulation (i.e., ascites requiring tapping despite use of diuretic or pleural effusion that either required tapping or is associated with shortness of breath).

15. Patients who have undergone major surgical procedure, open biopsy, or significant traumatic injury within 4 weeks of the start of protocol treatment
16. History of a bone marrow or solid organ transplant.
17. Any other condition that would, in the Investigator's judgment, contraindicate patient's participation in the clinical study due to safety concerns or compliance with clinical study procedures, e.g., infection/inflammation, intestinal obstruction, unable or unwilling to swallow medication, social/ psychological issues, etc.
18. Unable to undergo either contrast-enhanced magnetic resonance imaging (MRI) or contrast-enhanced computed tomography (CT).
19. Known history of human immunodeficiency virus (HIV) seropositivity. HIV testing is not required as part of this study.
20. Receiving treatment with medications that are known strong inhibitors or inducers of CYP3A4, and cannot be discontinued 7 days prior to the start of INC280 treatment and during the course of the study (refer to [Appendix 4](#)).
21. Receiving treatment with medications that are known CYP3A4 or CYP1A2, substrates with narrow therapeutic index, and cannot be discontinued before start of study treatment (refer to [Appendix 4](#)).
22. Unable to stop herbal/food supplements or treatments which are considered to be capable of significantly causing either PK or PD herb/food-drug interactions. From a PK point of view, refer to [Appendix 4](#). From a PD point of view, this definition includes any health authority approved herbal medication for HCC.
23. Have any of the following out-of-range laboratory values:
 - Hematology
 - Hemoglobin \leq 9g/dL (SI Units: 90g/L)
 - Platelet count $<$ 75 \times 10⁹/L
 - Absolute neutrophil count (ANC) $<$ 1.5 \times 10⁹/L
 - Biochemistry
 - Total bilirubin $>$ 2 mg/dL
 - AST/SGOT and/or ALT/SGPT $>$ 5 x upper limit of normal (ULN)
 - Serum creatinine $>$ 1.5 x ULN
 - Calculated or directly measured creatinine clearance $<$ 45 mL/min (refer to [Appendix 6](#) for the calculation)
 - Asymptomatic serum pancreatic amylase $>$ grade 2
 - Serum amylase grade 1 or grade 2 serum with signs and/or symptoms suggesting pancreatic or pancreatic injury (e.g. elevated P-amylase, abnormal imaging findings of pancreas, etc)
 - Serum lipase $>$ ULN
 - Fasting serum triglyceride level $>$ 500 mg/dL
24. Patients who have received any other investigational agents within a period of time that is less than the cycle length used for that treatment or equal to 4 weeks (whichever is shorter) prior to starting study drug and recovered from any side effects to grade 1 or less.

25. Pregnant or nursing (lactating) women, where pregnancy is defined as the state of a female after conception and until the termination of gestation, confirmed by a positive human chorionic gonadotropin (hCG) laboratory test.
26. Women of child-bearing potential, defined as all women physiologically capable of becoming pregnant, unless they are using highly effective methods of contraception during dosing and for 7 days after permanently discontinuing INC280 medication. Highly effective contraception methods include:
 - Total abstinence (when this is in line with the preferred and usual lifestyle of the patient. Periodic abstinence (e.g., calendar, ovulation, symptothermal, post-ovulation methods) and withdrawal are not acceptable methods of contraception
 - Female sterilization (have had surgical bilateral oophorectomy with or without hysterectomy) or tubal ligation at least six weeks before taking study treatment. In case of oophorectomy alone, only when the reproductive status of the woman has been confirmed by follow up hormone level assessment
 - Male sterilization (at least 6 months prior to screening). For female patients on the study the vasectomized male partner should be the sole partner for that patient.
 - Combination of any two of the following (a+b or a+c, or b+c):
 - a. Use of oral, injected or implanted hormonal methods of contraception or other forms of hormonal contraception that have comparable efficacy (failure rate <1%), for example hormone vaginal ring or transdermal hormone contraception.
 - b. Placement of an intrauterine device or intrauterine system
 - c. Barrier methods of contraception: Condom or Occlusive cap (diaphragm or cervical/vault caps) with spermicidal foam/gel/film/cream/vaginal suppository

In case of use of oral contraception women should have been stable on the same pill for a minimum of 3 months before taking study treatment.

Women are considered post-menopausal and not of child bearing potential if they have had 12 months of natural (spontaneous) amenorrhea with an appropriate clinical profile (e.g. age appropriate, history of vasomotor symptoms) or have had surgical bilateral oophorectomy (with or without hysterectomy) or tubal ligation at least six weeks ago. In the case of oophorectomy alone, only when the reproductive status of the woman has been confirmed by follow up hormone level assessment is she considered not of child bearing potential.

Sexually active males unless they use a condom during intercourse while taking drug and for 7 days after stopping study medication and should not father a child in this period. A condom is required to be used also by vasectomized men in order to prevent delivery of the drug via seminal fluid.

6 Treatment

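### Exclusion criterion 24 has its recovery clause in the wrong direction: inside the washout window it excludes the recovered patient and lets the unrecovered one pass

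*Protocol*

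**What the plan says.** Protocol Section 5.3 opens by making each listed item a bar to entry: "Patients eligible for this study must not meet" is how its rule begins. Section 5.1 enforces it: "The investigator or designee must ensure that only patients who meet all the following inclusion and none of the exclusion criteria are offered treatment".

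Criterion 24 has two parts. The exposure part concerns an earlier trial agent taken inside a washout window, set as the smaller of that agent's cycle length and 4 weeks. The recovery part is attached to it without a break: "whichever is shorter) prior to starting study drug and recovered from any side effects to grade 1 or less".

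Criterion 2, on local therapy, is the nearest comparison: "Previous local therapy completed less than 4 weeks prior to the dosing and, if present any related acute toxicity". The limit it then sets is above grade 1, so there the named state is unresolved toxicity.

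Nothing else in the two documents restates or corrects criterion 24. The exclusion list in the protocol summary omits it, and the SAP does not mention it.

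**The concern.** The recovery clause reads like a condition for entry, but it sits in a list of reasons for refusal. A site that follows the sentence exactly would turn away a patient whose earlier side effects have settled. The same sentence would give it no ground to turn away a patient whose side effects have not.

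The wording matters because the protocol makes it the operative standard. Section 9.2 requires monitors to verify adherence to the inclusion and exclusion criteria in full, and Section 12 allows no authorised deviations. A site reading for the apparent purpose and a site reading the words would decide differently on the same patient, and the monitor's check would favour the second.

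What is at stake is a clean baseline in a small single-arm study. Section 8.1.1 counts worsening of a pre-existing condition as an adverse event, and Section 10.5.3.2 includes worsening from baseline among treatment-emergent events. With no control arm, toxicity carried in from another agent that then worsens is hard to separate from an effect of INC280.

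**Working it through.** The plan gives no figure on this point, so the check is one of logic.

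Define two conditions from criterion 24:

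- A: another investigational agent was received inside the stated window.
- B: its side effects have recovered to grade 1 or less.

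The two are joined by *and*, with no *not* or *unless*. The literal rule is therefore: exclude if A and B. Two intentions are plausible:

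- Reading 1: exclude if A or not-B (recent exposure, or non-recovery).
- Reading 2: exclude if A and not-B (recent exposure with non-recovery).

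| Inside window (A) | Recovered (B) | Literal text | Reading 1 | Reading 2 |
|---|---|---|---|---|
| yes | yes | excluded | excluded | not excluded |
| yes | no | not excluded | excluded | excluded |
| no | yes | not excluded | not excluded | not excluded |
| no | no | not excluded | excluded | not excluded |

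Results:

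1. The literal text excludes 1 of 4 cells, and that cell is a recovered one. Neither cell with toxicity above grade 1 is excluded.
2. Against Reading 1, the literal text is wrong in 2 of 4 cells: both unrecovered cells.
3. Against Reading 2, it is wrong in 2 of 4 cells: both cells inside the window.
4. The inside-window, unrecovered patient is wrongly passed under both readings. That conclusion does not depend on which was meant.

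An illustration of the logic only: suppose the earlier agent was given in 21-day cycles and stopped 10 days before INC280. The window is the shorter of 21 days and 4 weeks (28 days), so 21 days, and 10 < 21 puts the patient inside it. With grade 3 toxicity still present, B is false and criterion 24 is not met. With recovery to grade 1, B is true and the patient is excluded.

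Criterion 2 names toxicity above grade 1, which is not-B, where criterion 24 names B. The two recovery clauses have opposite signs.

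**The case against.** The strongest case on the other side is that very few patients can be affected. Criterion 1 bars earlier systemic chemotherapy or targeted therapy for HCC, and criterion 3 bars c-MET and HGF agents. Criterion 5 bars most other malignancies in the previous 3 years, which largely rules out a recent trial agent for another cancer. Section 5.1 requires no prior systemic therapy and forbids parallel investigational studies. Criterion 17 lets the investigator exclude on safety grounds, and the laboratory limits in criterion 23 would catch some of the rest. Sites may also have read criterion 24 by its evident purpose. All of this stands and limits the reach. It does not repair the sentence, and criterion 17 sets no grade threshold.

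It can also be said that rewording is too late. The SAP introduction records that no patient would be enrolled after 25 December 2016. No planned analysis depends on the criterion: SAP Section 2.2 drops the per-protocol set, and SAP Table 2-1 ties no exclusion to it. That also stands. It moves the useful action from preventing wrong decisions to reporting whether any occurred.

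A reader might go further than the documents allow in four ways:

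- *That all recovered patients are excluded.* They are not. A recovered patient outside the window does not meet the criterion.
- *That the defect shifted the expansion dose.* Table 14-18 shows the model's recommendation moving from 600 to 500 mg bid when 1 rather than 0 of 6 patients has a qualifying event. That table holds hypothetical scenarios based on the model alone, and its footnote leaves the actual dose to a review of all data. A carried-over toxicity would have to worsen and be wrongly attributed to INC280, since Section 6.2.3 requires the investigator to judge the event related to it. The dose decision was already taken, with expansion under way from December 2013 at 600 mg bid in capsules. The table does not measure the effect of this wording.
- *That criterion 2 settles the intended reading.* It settles only the sign. Its own clauses are loosely joined, so it does not choose between Readings 1 and 2.
- *That the amylase items in criterion 23 show the same inversion.* One covers asymptomatic elevation above grade 2. The other reads "Serum amylase grade 1 or grade 2 serum with signs and/or symptoms suggesting pancreatic or pancreatic injury", which is garbled and leaves symptomatic elevation above grade 2 unnamed. That is a coverage gap, partly met by criteria 10 and 17 and the lipase limit. At most, these bullets need to be reconciled with each other.

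**Conclusion.** Criterion 24 is wrong as written. This is a drafting error in an operative eligibility rule. The conclusion rests only on the literal sentence and on the rule that opens Section 5.3; it holds under both plausible intentions.

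Its practical size is small. The documents do not say how many patients had an earlier investigational agent, so no count can be given, but the other criteria leave room for few. The sample size, the error rates and the time-to-progression analysis are untouched. What remains is a possible safety-baseline question for individual treated patients, which the documents cannot answer.

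**What to change.** 1. State which reading of criterion 24 was intended: recent exposure or non-recovery, versus recent exposure with non-recovery. Then correct the sign of the recovery clause and reconcile it with criterion 2. The washout length and the grade limit stay as they are; neither is questioned here.
2. Because enrolment is closed, check the treated patients and report in the clinical study report whether any entered with unresolved toxicity from an earlier investigational agent. Prior antineoplastic therapy and medical history are already collected at screening (Protocol Section 7.1.2.3), so the check starts from existing data. If there are none, one sentence suffices. If there are any, identify them so that their adverse events can be read against baseline.
3. If the section is being edited anyway, reconcile the two amylase bullets of criterion 23.

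The cost is a wording correction and a short eligibility check in a study planned for approximately 56 patients. No analysis has to be rerun.
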